### 4.2 Scientific Rationale for Study Design

#### 4.2.1 Rationale for primary, secondary and exploratory endpoint

The primary objective is to describe the gene profile in tissue in *EGFR*m locally advanced or metastatic NSCLC patients post on 1L Osimertinib failure, which could help clinicians provide the following treatment strategy.

The secondary objective is to describe the gene profile in plasma, to assess the concordance of plasma and tissue, and the percentage of pathology transformation. Gene profile in plasma and the percentage of pathology transformation will be detected and analysed by NGS and IHC, respectively. Concordance of plasma and tissue is to explore whether plasma can be substitute for tissue when patients cannot accept tissue biopsy, which is defined as sensitivity, specificity, PPV and NPV of representative genes. According to the assay performance, sensitivity 80% is acceptable. If the point estimate for sensitivity is  $\geq 80\%$ , plasma samples are supposed to be consistent with tissue sample for NGS testing.

In the case of sufficient tissue samples, the exploratory endpoints is further to assess prevalence of MET amplification by FISH in tissue samples, the concordance of MET amplification

between FISH testing in tissue samples and ddPCR testing in blood samples, the prevalence of MET overexpression by MET IHC testing and the overlap ratio of prevalence between MET amplification by FISH and MET overexpression by MET IHC. The prevalence data of MET overexpression by MET IHC and MET amplification by FISH in post 1L Osimertinib resistance patients in China are very limited.

Tissue were unavailable for some patients post 1L Osimertinib and ddPCR testing will offer alternative method for MET amplification testing in blood samples. Concordance of MET amplification testing between ddPCR in plasma samples and FISH in tissue samples is to explore whether plasma can be substitute for tissue when patients cannot accept tissue biopsy, which is defined as sensitivity, specificity, PPV and NPV of representative genes.

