**Table 13 Validation information of plasma sample detected by ddPCR**

Sample type	Plasma
-------------	--------

Sample requirement	1. non- hemolysis 2. extraction DNA $\geq 0.5$ ng/ $\mu$ l 3. total DNA content $\geq 25$ ng
Assay	MET gene amplification testing assay -ddPCR
Cut off	MET/CEP7 $\geq 2$

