3. ANALYSIS SETS

3.1 Definition of analysis sets

The following populations are defined:

Table 1 Populations for Analysis

Population/Analysis Set	Description
Enrolled	All participants who sign the ICF
FAS	All participants who meet the required inclusion/exclusion criteria and have valid Gene data from both plasma and tissue. CCI

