5. ANALYSIS METHODS

5.1 General Aspects

All statistical analyses will be completed using SAS version 9.4 or later, and R 4.0 or later. Descriptive statistics will be provided for all variables, as appropriate. Continuous variables will be summarized by the number of observations, mean, standard deviation, median, interquartile range (Q1, Q3), minimum, and maximum. Categorical variables will be summarized by frequency counts and percentages for each category. The 95% confidence interval (CI) will be calculated as appropriate.

The analyses will be based on Full analysis set (FAS), which will include all patients who meet the required inclusion/exclusion criteria and have valid Gene data from both plasma and tissue.

Patients missing tissue or plasma NGS data or MET data will not be used for concordance analysis, but only for individual tissue or plasma analysis.

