5.1.1 Handling of Missing Data

Missing data will not be imputed unless otherwise specified elsewhere in the SAP.

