5.4.2 Secondary Endpoint

The secondary objective is to assess gene profile in plasma, concordance of plasma and tissue and the percentage of pathology transformation will be analysed by NGS method and IHC. All gene alterations in plasma(e.g., gene mutation, amplification, deletion, fusion, etc.) detected will be observed. Proportion of Gene X alteration(%) = (number of patients with Gene X alteration, which is an example of a certain gene)/(total number of patients in the FAS)×100%. Some cases which patients have more than one gene alteration need to be considered, therefore percentages may not add up to 100%.

Using selected representative genes to measure the concordance. The representative genes should include the top 20 mutated genes observed in tissue samples. Concordance of Gene X in plasma and tissue is defined as sensitivity, specificity, positive predictive value (PPV), negative predictive value (NPV), and overall percent agreement between plasma and tissue results., Tissue sample is the reference standard.

Sensitivity=(number of patients with positive result in both plasma and tissue)/(total number of patients with positive result in tissue samples)×100%;

Specificity=(number of patients with negative result in both plasma and tissue)/(total number of patients with negative result in tissue samples)×100%.

[figure not shown]
PPV (%)=(number of patients with positive result in both plasma and tissue)/(total number of patients with positive result in plasma samples)×100%;

NPV (%)=(number of patients with negative result in both plasma and tissue)/(total number of patients with negative result in plasma samples)×100%.

Overall percent agreement(%) =(number of patients with same result <positive or negative> in both plasma and tissue)/(total number of patients in FAS)×100%

Pathology transformation defines as pathological type of lung cancer change, which will be confirmed by pathologists. Number and percentage of patients with pathology transformation will be summarized. Proportion of pathology transformation(%) = (number of patients with pathology transformation)/(total number of patients in the FAS)×100%.

CCI

CCI

[REDACTED]

[REDACTED]
[REDACTED]
[REDACTED]

[REDACTED]

[figure not shown]
		[REDACTED] [REDACTED]	[REDACTED]	
[REDACTED]	[REDACTED]			
	[REDACTED]			
[REDACTED]				

[REDACTED]
[REDACTED]
[REDACTED]
[REDACTED]
[REDACTED]
[REDACTED]

[REDACTED]
[REDACTED]
[REDACTED]
[REDACTED]
[REDACTED]
[REDACTED]
[REDACTED]
[REDACTED]

CCI

CCI

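### Plasma sensitivity is planned on valid pairs only, so plasma NGS failures in tissue-positive patients are not visible when the result is used to ask whether plasma can replace tissue

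*SAP*

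**What the plan says.** The sensitivity formula in SAP 5.4.2 has as its denominator the "total number of patients with positive result in tissue samples". Taken alone, that wording would keep a tissue-positive patient whose plasma test failed. Three other rules in the SAP take that patient out:

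- SAP 3.1 defines the FAS as "All participants who meet the required inclusion/exclusion criteria and have valid Gene data from both plasma and tissue". Protocol Table 3 has the same definition.
- SAP 5.1 says "Patients missing tissue or plasma NGS data or MET data will not be used for concordance analysis" and keeps such patients only for single-sample summaries.
- SAP 5.1.1 says "Missing data will not be imputed unless otherwise specified elsewhere in the SAP", so a failed plasma test is not converted to a negative.

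The purpose is in Protocol 4.2.1: "Concordance of plasma and tissue is to explore whether plasma can be substitute for tissue when patients cannot accept tissue biopsy". Protocol 7.3.1 repeats it. Section 4.2.1 also sets the benchmark, "According to the assay performance, sensitivity 80% is acceptable", and treats a point estimate at or above that figure as showing that plasma NGS is consistent with tissue.

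The visible text does not define a valid result, does not plan to report a plasma failure rate, and has no analysis in which failed plasma counts as not detected.

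**The concern.** Two questions share one number. The first is how well plasma and tissue NGS agree when both assays work; valid pairs answer it. The second is what share of tissue-detectable alterations would be found if only blood were available. A patient without a biopsy whose plasma assay fails has no alteration reported from that test, and the planned figure leaves such patients out.

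If any tissue-positive participant has a failed plasma NGS result, the planned sensitivity will be higher than the share that answers the second question. Because the 80% line is applied to a point estimate, a modest difference could change which side of the line a gene falls on. A reader would have no failure rate beside the estimate from which to judge this.

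**Working it through.** **Inputs from the documents.** The sensitivity denominator (SAP 5.4.2), the both-valid restriction (SAP 3.1 and 5.1), no imputation (SAP 5.1.1), the 80% point-estimate line (Protocol 4.2.1), and 200 enrolled with about 180 profiled after 10% drop-out (SAP 2.2).

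**Input not in the documents.** f, the share of tissue-positive patients whose plasma NGS fails. It is assumed here at 2%, 5%, 10% and 15%.

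**Step 1: the plan's own figures.** These reproduce.

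- The exact (Clopper-Pearson) 95% interval for 40/200 is 14.7% to 26.2%, as stated, and the other four table rows also match.
- 1 − 0.99^200 = 86.6%, against a stated 86%.
- 200 × (1 − 0.10) = 180.

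The plan states no expected sensitivity and no plasma failure rate, so there is no figure of that kind to reproduce.

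**Step 2: the relation.** Let N be all eligible tissue-positive patients, n those among them with valid plasma, and x those positive in both samples. Then f = (N − n)/N, and

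x/N = (x/n) × (n/N) = valid-pair sensitivity × (1 − f).

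This is an identity. Because f is defined among tissue positives, nothing need be assumed about why plasma fails.

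**Step 3: a reported 80%.** The third column is 0.80/(1 − f).

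| Assumed f | 0.80 × (1 − f) | Valid-pair figure needed for 80% of all tissue positives | Gap at 80% |
|---|---|---|---|
| 0% | 80.0% | 80.0% | 0 points |
| 2% | 78.4% | 81.6% | 1.6 points |
| 5% | 76.0% | 84.2% | 4.0 points |
| 10% | 72.0% | 88.9% | 8.0 points |
| 15% | 68.0% | 94.1% | 12.0 points |

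**Step 4: whole-patient illustration.** Take 40 tissue-positive patients (20% of 200, the plan's own planning incidence).

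- Two plasma failures (f = 5%): 31/38 = 81.6% (95% CI 65.7% to 92.3%) on valid pairs; 31/40 = 77.5% (61.5% to 89.2%) with failures kept.
- Four plasma failures (f = 10%): 29/36 = 80.6% (64.0% to 91.8%) on valid pairs; 29/40 = 72.5% (56.1% to 85.4%) with failures kept.

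In each pair the first figure meets the 80% line and the second does not. The numerators were chosen as the smallest that pass on valid pairs, so these are boundary cases, not forecasts. If failure is unrelated to tissue status, f = 10% would mean 20 plasma failures among 200 tissue-valid patients, which is the whole of the planned loss of 20. The 15% row would exceed that loss.

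**The case against.** The strongest reply is that nothing is miscalculated. Sensitivity among paired valid results is a standard agreement measure, Protocol 4.2.1 links the 80% figure to assay performance, its conclusion is worded as consistency of NGS testing, and the substitution aim is only to explore. A failed test is also recognisable as a failure, whereas a false negative is not, so reporting the failure rate separately is as defensible as counting failures as not detected. All of this stands. It is why the valid-pair table should remain and why the extra row is supplementary. It does not explain why no failure rate is planned beside a figure that the same section uses for substitution.

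Four stronger readings are tempting, and the documents do not support them.

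- *Plasma failure is informative.* Protocol Table 13 requires "total DNA content $\geq 25$ ng", which might suggest that plasma with little DNA is rejected. That rule is for ddPCR at a different laboratory. The plasma NGS requirements in Appendix F are 10 ml of blood and a depth of at least 1000x, with no DNA-yield rule. A sample that meets the depth requirement but carries the variant below the detection limit would be a valid negative and already counts against sensitivity.
- *The 10% is a plasma failure rate.* Protocol 8.1 attributes it to loss to follow-up. Tissue can also fail, since Appendix F requires ten slides and at least 20% tumour content.
- *The background 15% for MET amplification gives the number of tissue positives.* Protocol 2.2 reports 15% from plasma; the tissue study beside it found 7%.
- *Crossing 80% shows a large effect.* The intervals in Step 4 overlap heavily. The reversals partly reflect a rule based on a point estimate in a small group.

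**Conclusion.** The point holds as a mismatch between the planned estimate and one of its stated uses. The exclusion is explicit in SAP 3.1 and 5.1. The direction is certain if at least one eligible tissue-positive participant has failed plasma NGS and at least one alteration is detected in both samples.

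The size is unknown because the documents give no f. A reported 80% would correspond to 78.4%, 76% or 72% at assumed failure shares of 2%, 5% or 10%, and to 80% if no plasma test fails. A reader might infer that the planned sensitivity is wrong, or that it is known to be overstated; neither follows. It is a valid agreement measure, and the gap arises only for the substitution question.

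Nor does it follow that every statement on substitution must rest on the failures-counted figure alone. Showing both is enough. No conclusion is drawn about ddPCR against FISH, whose analysis text is redacted. This is a cheap improvement to a descriptive secondary endpoint.

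**What to change.** In SAP 5.4.2:

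1. Keep the valid-pair concordance table as planned.
2. State what counts as a failed or invalid plasma NGS result, and report the plasma failure rate among eligible participants with valid tissue results.
3. Add one supplementary sensitivity row per representative gene. Its denominator is all eligible tissue-positive participants, with failed or invalid plasma counted as not detected. Confine the row to sensitivity, because counting failures as negative would flatter specificity.
4. Present both estimates beside any statement that plasma can substitute for tissue, and state which of them the 80% line in Protocol 4.2.1 refers to.

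The cost is a few lines of SAP text and one more table row per gene. No new data are needed, because SAP 5.1 already keeps these patients' tissue results for single-sample analysis. The downside is a possibly less favourable figure. If no plasma test fails, the two rows coincide.
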